3. The risk of seizure during TMS is a well-studied one. In normal subjects, it is an extremely rare occurrence. Repetitive TMS can induce a seizure in the absence of pre-existing brain lesions, epilepsy, or other seizure risk factors, both in patients and healthy subjects. From the several thousands of studies that have used TMS to date, a total of 16 cases have been reported, of which 9 cases occurred after the 1998 safety guidelines. Based on the available data, the reported risk of seizures is less than 1 in 1000 for repetitive TMS. In individuals with a known history of seizures, the occurrence of a seizure temporally proximate to TMS is very uncommon; the overall rate of any seizure associated with single- and paired-pulse TMS in those with known epilepsy is only 0.8-1.8%, and the risk if no changes were made in anticonvulsant medications is only 0.0-0.4%. Similarly, even with rTMS in patients with known epilepsy, the crude risk of seizures associated with TMS was about 1.4%, and almost all seizures were identical to those typically experienced by the individual, making it unclear whether seizures were causally related to the TMS or not.¹⁷ Almost all reported seizures predated the advent of current safety guidelines, to which our proposed study will adhere closely. No instances of status epilepticus have ever been reported in association with TMS.
4. Syncope can occur due to anxiety and psycho-physical discomfort during testing and treatment with TMS. This is reported less than seizure activity but the true number may be higher due to underreporting. Subjects will be monitored for feeling any signs or symptoms of a pending syncopal event (i.e. feeling "dizzy, lightheaded or going to pass out"). TMS will immediately be stopped and the subject will be assisted.
5. TMS could induce short-term changes in memory, attention, and other cognitive functions. This is a theoretical risk, as none of the safety studies conducted has found such side effects. However, because the understanding of brain connectivity in the population of patients with PNH is limited, the risk for these patients in particular is not clear.

6. Acute psychiatric effects such as mania and delusions have been described in patients with medically refractory depression or bipolar disorder who received rTMS. This seems to be a rare complication (incidence <0.15% of patients), and individuals with a current diagnosis of a mood disorder will be excluded from this study.
7. The possibility of dental pain during rTMS has been reported. This potential adverse effect would occur during the stimulation itself. Subjects will be asked to report any such discomfort immediately to the investigator, who would terminate the stimulation session. The subject will be encouraged to seek a dental evaluation, since this is a very rare occurrence but may point to the presence of a cavity that may require care. This adverse effect is not expected to lead to any lasting problems or complications.

Protection Against Risks

As described above, no significant health risks are expected from the neuroimaging procedures in this study. Standard research MRI safety procedures in place at Beth Israel Deaconess Medical Center will be used, including safety questionnaires prior to scanning (asking about surgeries, metal implants, shrapnel, etc.).

Multiple safety precautions are in place for the TMS portion of the study, including the design of the stimulation protocol in a way that is well within guidelines for rTMS safety, is consistent with prior studies that have demonstrated safety in a population of patients with refractory epilepsy.⁴ All TMS sessions will be conducted in the presence of a board-certified neurologist who has been trained in the safe and efficient administration of TMS and in basic life support and in the recognition and treatment of seizures, syncope, and other neurological and medical emergencies. A fully equipped and regularly checked “crash cart” is available at Beth Israel Deaconess Medical Center for potential emergencies. This emergency equipment also includes oxygen supply, IV line supplies, and emergency medications in the event of a convulsion. Subjects will be monitored in detail during and after delivery of TMS, using an approach drawn directly from suggested guidelines.

Confidentiality will be preserved at all times, using standard HIPAA-compliant clinical measures already in place at the institution. As described above, only the PI and PI's research assistant will be aware of individual subject identities and have access to code number assignments.

The PI, a board-certified neurologist and clinical neurophysiologist, will be responsible for the patient's medical welfare should any unexpected adverse events occur during these research activities, and will intervene as appropriate.

Risk-Benefit Analysis

Given the limited foreseeable risks described above, the procedures to be put in place to protect against these risks, and the potential benefits to the subjects and others as described above, the risk/benefit ratio is acceptable for subjects.

Data and Safety Monitoring

All adverse effects, regardless of attribution to study procedures, will be collected from the start of the experimental protocol to the end of study participation, using standard adverse event forms. Subjects will be asked in an open-ended way about the presence of any adverse events; intensity will be graded

for each adverse event; and the likelihood that the event is or is not related to study participation will be noted.

A data safety monitoring board, comprising three investigators with expertise in the field, experience in conduct of human subject research and statistical knowledge, independence from the direct management of this study, and freedom from conflict of interest or commitment, will be appointed by the PI. A chairperson will be appointed and will be responsible for overseeing the meetings, developing the agenda, and summarizing the meeting. The chairperson will be the contact person for the DSMB.

The DSMB will meet prior to the enrollment of the first subject to review the research protocol, informed consent documents and plans for safety and data monitoring of the study. The DSMB will determine the risks and benefits to research subjects, protection and safety of the subjects and offer suggestions for improving the study design. In addition, the Board will reach agreement on the data that will be required for review. Determination of the schedule of future meetings, appointment of the chair and voting members, who receives minutes, and the signing of conflict of interest statements will occur during pre-enrollment meeting. The pre-enrollment Board meeting may result in modification of the safety plan provided in the CCI application. If the DSMP is changed at the first meeting of the Board, the new plan will be submitted to the BIDMC Committee on Clinical Investigations (CCI).

The DSMB will meet at least annually, and may decide to meet more frequently if necessary. The chairperson may call ad hoc meetings depending on safety or efficacy concerns. Meetings may be conducted by teleconference or over e-mail at the request of Board members. The DSMB will review interim data to detect evidence of efficacy or adverse effects to determine if the trial should continue as originally designed, should be changed or should be stopped based on the data. The DSMB will evaluate the progress of the trial, including periodic assessments of data quality/completeness, recruitment goals, protocol adherence, accrual and retention of participants and other factors that may affect the study outcome. The DSMB will protect confidentiality of the study participants, trial data and results of the monitoring.

Specifically, at each meeting, the PI will provide the Board with the information that was determined at the pre-enrollment meeting. The Board may then, according to a plan determined at the pre-enrollment meeting, review the following:

- a. determine adherence to treatment plan
- b. review interim analysis, if applicable, and determine specific data to be analyzed
- c. evaluate end point/stop point rules
- d. review protocol violations and deviations to assess adequacy of study
- e. ensure documentation of informed consent
- f. enrollment
 - (1) followed eligibility criteria
 - (2) enrollment numbers
 - (3) visit compliance
 - (4) screening failure information
- g. review IND/IDE information
- h. discuss investigator or key personnel changes
- i. review completeness and quality of data collection forms
- j. evaluate the aggregate analysis of adverse events/serious adverse events

- k. review vital signs, clinical tests, etc.
- l. review confidentiality

The major outcomes following data review include:

- 1. continuing the trial unchanged
- 2. modify the protocols and/or consent form
- 3. terminate the trial

Minutes from the meeting will be maintained. The investigator will not be present for at least part of this meeting. Following the Board meeting, a report will be provided to the investigator, the BIDMC CCI, and if necessary, study participants. The report will indicate whether the study should continue as originally designed, whether the study should be modified to protect patient safety or whether the study should be terminated.

All records regarding this research project will be stored in the locked office of the PI, in the Comprehensive Epilepsy Center of BIDMC. The data will be stored on paper and on secure computers protected with passwords. The subjects' identity will not be disclosed in publications or presentations. The records of the research project are open only to authorized monitors from the BIDMC CCI, the DSMB, and the FDA. All applicable local regulatory requirements relating to the reporting of adverse events will be followed during this study.

B6. RECRUITMENT AND CONSENT PROCEDURES

Recruitment

We will recruit subjects from our Comprehensive Epilepsy Center and through referrals from other clinicians. The patients may be initially informed on of several ways:

- The investigator will briefly explain this study to them, and ask if they would like to hear more about it.
- The potential subject may be approached at the time of a clinic appointment. At that time, the investigator may briefly explain the study.
- The potential subject will receive a telephone call from an investigator on this study.

In either case, a "voided copy" of the consent form will be mailed to the potential subject, or handed to them in person if possible, prior to meeting for informed consent. This will allow adequate time to read the consent form in detail, record questions, and consider the option of enrollment.

Consent

Subjects will be contacted and introduced to the concept of the study. Those potential subjects who do not express interest in the study will be thanked and no further recruitment efforts will be pursued. For those who do express interest in the study, they will be given a copy of the consent form. The study procedure, risks and benefits, and alternatives will be explained by an MD designated to obtain consent on the study, and subjects will be encouraged to ask questions and discuss any concerns. The Investigator will then obtain informed consent and each subject will be given a copy of the signed informed consent form. Potential subjects will be reminded that participation in the study is completely voluntary and that they are free to terminate the study at any time, and that the Principal

Investigator will be available to contact for any questions that may arise during the study period.

Subject Protection

No vulnerable populations are included in this study.

B7. STUDY LOCATION

Privacy

In all portions of the study, provisions will be made to ensure that the privacy of the subjects are protected throughout. Recruitment of the subjects will take place by phone or in person in a private examination room with the door closed in a secure clinical area. If subjects wish not to speak on the phone or to be contacted at a different number or at a later time, their preferences will be accommodated. The information collected during recruitment will be limited only to the minimum amount of data necessary, namely to confirm that the subjects actually are eligible for the study according to the inclusion/exclusion criteria. The consent process will occur in person in a private examination room with the door closed in a secure clinical area.

Physical Setting

Recruitment and consent will occur at the Comprehensive Epilepsy Center of Beth Israel Deaconess Medical Center (PI's location).

MRI scanning and TMS experiments will be performed at the Berenson-Allen Center for Noninvasive Brain Stimulation at Beth Israel Deaconess Medical Center.

Data analysis will occur at BIDMC (PI's location), and the Berenson-Allen Center for Noninvasive Brain Stimulation at BIDMC (laboratory of [name], PhD (Co-investigator). For data analysis, imaging datasets will be transferred either in person to the collaborating sites or electronically using secure Web-based file transfer protocols

B8. DATA SECURITY

Data obtained from our experiments will be assigned specific identifying code numbers so that they can be processed, analyzed, and reported without direct access to subjects' identities. Only the following individuals at Beth Israel Deaconess Medical Center need to know individual subject identities, and will have access to the code number assignments: the PI and the PI's research assistant. Electronic data containing PHI will be kept on a secure server behind the BIDMC firewall.

B9 Multi-Site Studies

Is the BIDMC the coordinating site? Yes No N/A

Is the BIDMC PI the lead investigator of the multi-site study? Yes No N/A

B10 Dissemination of Research Results

The study staff will verbally thank research subjects at the conclusion of each study visit. At the end of the study, study staff will ask the subject if he or she is interested in knowing the results of the study. If the participant is interested, preliminary results will be reviewed during a phone call scheduled with the Principal Investigator.

Literature Cited

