We will recruit 30 subjects from our Comprehensive Epilepsy Center and through referrals from other clinicians. The patients may be initially informed on of several ways:

- The investigator will briefly explain this study to them, and ask if they would like to hear more about it.
- The potential subject may be approached at the time of a clinic appointment. At that time, the investigator may briefly explain the study.
- The potential subject may receive a telephone call from an investigator on this study. At the time of the telephone call, the investigator may briefly explain the study.

In either case, a “voided copy” of the consent form will be mailed to the potential subject, or handed to them in person if possible. This will allow adequate time to read the consent form in detail, record questions, and consider the option of enrollment.

At the time of consent, randomization will occur based on order of enrollment into the study using a computer-generated randomization table. Subjects will be randomized into three treatment groups. In Group 1, we will target continuous low frequency rTMS (1 Hz, at 95% resting motor threshold (RMT), over ten daily 30-minute sessions) to cortical regions that are highly correlated with the epileptogenic MTL. In Group 2, we will target high-frequency rTMS (10 Hz, 110% RMT, over ten daily 30-minute sessions) to cortical regions that are highly anti-correlated with the epileptogenic MTL. Group 3 will receive sham TMS as a control intervention (using a sham coil over a highly correlated cortical region, over ten daily 30-minute sessions).

Subjects will be blinded to their treatment group assignment. Subjects and family members or caregivers will be asked to maintain diaries of all seizures and possible adverse effects, which will be reviewed by an investigator blinded to treatment group assignments.

1. MRI scanning and data analysis (One hour to complete, on one day)

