After subjects have been randomized, they will undergo brain connectivity imaging. We will obtain BOLD functional MRI in 30 patients with refractory MTLE during the task-free resting state. We will systematically determine for each patient the neocortical foci that are highly correlated and anticorrelated to the epileptogenic MTL by using a population-based map of normal resting-state MTL connectivity as a seed network of interest. This will allow us to selectively identify regions of relevant correlation to the MTL that fall within easily accessible areas for rTMS based on our technical experience (including most of the frontal, parietal, and lateral temporal cortex, while avoiding the frontopolar and occipital regions due to head positioning and the need for eyeglasses worn to calibrate the TMS neuronavigation system). **Subject time: 1 hour.**

2. Baseline seizure diary (12 weeks)

Subjects will keep a baseline seizure diary for 12 weeks, during which time connectivity analyses and tMS target creation will be performed by the investigators. **Subject time: 12 weeks.**

3. Pre-rTMS EEG (One hour to complete, on one day)

EEG recording of interictal epileptiform discharge (IED) frequency will occur prior to first TMS session. **Subject time: 1 hour.**

4. Experimental Design for rTMS (On average one and a half hours to complete, on ten consecutive weekdays)

We will conduct a controlled assessment of two different rTMS protocols applied to specific cortical targets (derived from connectivity imaging results) in the 30 patients with medically refractory MTLE. The cohort had been randomized into three treatment groups. In Group 1, we will target continuous low-frequency rTMS to cortical regions that are highly correlated with the epileptogenic MTL. In Group 2, we will target high-frequency rTMS to cortical regions that are highly anti-correlated with the epileptogenic MTL. Group 3 will receive sham TMS as a control intervention. Each subject will have ten 30 minute rTMS sessions over a two-week period, ten consecutive weekdays. **Subject time: 1.5 hours per rTMS session. 10 rTMS sessions.**

5. Post-rTMS EEG (One hour to complete, on one day)

EEG recording of interictal epileptiform discharge (IED) frequency will occur after the last TMS session. **Subject time: 1 hour.**

6. Follow-up seizure diary (12 weeks)

Subjects will keep a follow-up seizure diary for 12 weeks post rTMS. **Subject time: 12 weeks.**

7. Final EEG (One hour to complete, on one day)

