EEG recording of interictal epileptiform discharge (IED) frequency will occur 12 weeks after the last rTMS session. **Subject time: 1 hour.**

At 12-week follow-up, the primary outcome measure will be seizure frequency compared to baseline, and the secondary outcome measure will be IED frequency compared to baseline. Subjects will be blinded to their group assignment, as will the investigator who reviews seizure diaries and determines IED frequency on EEG. Adverse events will be tracked closely throughout the study protocol.

Follow-Up

The investigators will conduct a controlled assessment of the response to the initially chosen rTMS protocol and determine if the subject may be appropriate for further rTMS. Investigators may invite subjects back to repeat the study procedures 2-7. The follow-up rTMS protocol chosen by investigators will depend on the subject's response, or lack thereof, to the previously performed protocol.

Subjects who are invited back for further rTMS sessions and choose to return will undergo the following specific procedures:

1. Baseline seizure diary (12 weeks)

Subjects will keep a baseline seizure diary for 12 weeks, during which time connectivity analyses and tMS target creation will be performed by the investigators. **Subject time: 12 weeks.**

2. Pre-rTMS EEG (One hour to complete, on one day)

EEG recording of interictal epileptiform discharge (IED) frequency will occur prior to first TMS session. **Subject time: 1 hour.**

3. Experimental Design for rTMS (On average one and a half hours to complete, on ten consecutive weekdays)

Based on analyses of the subject's response to the initially assigned rTMS protocol, the alternative protocol (either low-frequency rTMS to cortical regions that are highly correlated with the epileptogenic MTL or high-frequency rTMS to cortical regions that are highly anti-correlated with the epileptogenic MTL) will be used. Each subject will have ten 30 minute rTMS sessions over a two-week period, ten consecutive weekdays. **Subject time: 1.5 hours per rTMS session. 10 rTMS sessions.**

4. Post-rTMS EEG (One hour to complete, on one day)

EEG recording of interictal epileptiform discharge (IED) frequency will occur after the last TMS session. **Subject time: 1 hour.**

5. Follow-up seizure diary (12 weeks)

Subjects will keep a follow-up seizure diary for 12 weeks post rTMS. **Subject time: 12 weeks.**

6. Final EEG (One hour to complete, on one day)

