Functional connectivity imaging analyses will be performed using an in-house software toolbox, according to methods previously described.⁸ Briefly, functional images will be realigned, normalized, and co-registered to an anatomic image. Functional images will be segmented and BOLD signal extracted. A band-pass frequency filter (0.01 Hz < f < 0.1 Hz) will be applied, and Gaussian smoothing performed (6 mm full width at half maximum). Several possible confounding sources of noise will be removed. A population-based map of right or left MTL connectivity derived from normal

individuals, with rTMS-accessible regions of cortex removed, will be used as a seed network of interest for analyses. Color-coded functional connectivity maps will be created for each subject, showing correlations to the average BOLD signal time series of the MTL network, subject to a voxel-wise statistical threshold of $p < 0.001$ and cluster thresholding with an intensity cutoff.

Stimulation target creation

For each subject, a neocortical target for TMS will be created based on the functional connectivity results and the subject's group assignment (significantly correlated region for Groups 1 and 3, and significantly anti-correlated region for Group 2). The target will be manually outlined using MRICroN software¹³ as a discrete region of cortex that demonstrates significant connectivity to the MTLE network seed, based on the analyses derived above. Targets will then be transferred directly into the TMS neuronavigation software for visualization during the stimulation paradigm.

rTMS protocol

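### Randomizing at consent, before targets exist, leaves randomized but untreated subjects with no dated outcomes for the intention-to-treat analysis

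*Combined protocol and SAP*

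**What the plan says.** **Order of events.** B3.A, Subject Enrollment, sets allocation at consent: "At the time of consent, randomization will occur based on order of enrollment into the study using a computer-generated randomization table". Item 1 of the same section puts the scan afterwards: "After subjects have been randomized, they will undergo brain connectivity imaging". Item 2 places the target work later still: "Subjects will keep a baseline seizure diary for 12 weeks, during which time connectivity analyses and tMS target creation will be performed". Item 4 speaks of the cohort as already randomized when stimulation begins.

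**What a target must satisfy.** Under B3.B, Stimulation target creation, "a neocortical target for TMS will be created based on the functional connectivity results" and on the assigned group: "significantly correlated region for Groups 1 and 3, and significantly anti-correlated region for Group 2". The outline is drawn by hand. Under Functional connectivity analysis, the maps must pass a voxel-wise threshold of p < 0.001 and "cluster thresholding with an intensity cutoff". Item 1 of B3.A further limits targets to cortex that the coil can reach, which leaves out the frontopolar and occipital regions.

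**How outcomes are dated.** Item 3 places the baseline EEG before the first stimulation session. Item 6 reads "Subjects will keep a follow-up seizure diary for 12 weeks post rTMS", and item 7 reads "EEG recording of interictal epileptiform discharge (IED) frequency will occur 12 weeks after the last rTMS session". The Sample Size Justification in B3.B plans an intention-to-treat analysis by ANOVA with Group and Time (two levels, repeated measures). It names no method for missing values. No section gives a rule for a randomized subject who has no qualifying region.

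**The concern.** At least 12 weeks and one selection step lie between randomization and the first session. Anyone who fails that step, or leaves during the interval, counts as randomized but has no date from which to start the follow-up diary or the final EEG. The baseline EEG may be missing too, because it is also tied to the first session. The primary comparison could then rest on those who turned out to be treatable, not on all those randomized.

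The selection step is also not the same in every arm. Group 2 needs an anti-correlated region; Groups 1 and 3 need a correlated one. Whether a borderline region qualifies is judged with the arm known. With about 10 subjects per arm, each one excluded is about 10% of an arm, and loss that depends on the arm is not protected by randomization.

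**Working it through.** **1. The plan's own figure.** The Sample Size Justification states 27 needed and 30 enrolled. The 27 is reproduced by a between-group test in a repeated-measures ANOVA with the 56% entered as Cohen's f = 0.56, 3 groups, 2 time points and an assumed within-subject correlation of 0.5:
- noncentrality = N × f² × m / (1 + (m − 1) × rho) = 27 × 0.3136 × 2 / 1.5 = 11.29
- with 2 and 24 degrees of freedom, power is 0.813

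Under the same model power is 0.859 at 30 and 0.795 at 26. Losing 3 subjects from Group 2 alone leaves about 0.83, if both active arms have equal effects. These values only illustrate the effect of losing subjects. They show that lost power is not the main harm here.

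**2. Which measures survive for a randomized but untreated subject.**

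| Measure | Dated from | Defined without rTMS? |
|---|---|---|
| Baseline diary | Enrollment phase | Yes |
| Pre-rTMS EEG | First session | No |
| Follow-up diary | End of rTMS | No |
| Final EEG | Last session + 12 weeks | No |

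The primary outcome lacks its follow-up value. The secondary outcome may lack both values. A two-level repeated-measures ANOVA needs both values for each subject.

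**3. How often the case could arise.** The documents give no target-failure rate, so p is assumed. If p applies equally in all arms, the expected number is 30p and the chance of at least one is 1 − (1 − p)^30. If only Group 2 is affected, the chance is 1 − (1 − p)^10.

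| Assumed p | Expected in 30 | At least one in 30 | At least one in Group 2 (n = 10) |
|---|---|---|---|
| 2% | 0.6 | 45% | 18% |
| 5% | 1.5 | 79% | 40% |
| 10% | 3.0 | 96% | 65% |

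The chance passes one half at p = 1 − 0.5^(1/30) = 2.3% when all arms are affected, and at 1 − 0.5^(1/10) = 6.7% when only Group 2 is. Subjects who leave before session 1 for other reasons would add to these figures.

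**4. Which comparisons could be affected by arm-dependent loss.**
- Low-frequency vs sham: same criterion in both arms, so no.
- Low- vs high-frequency: criteria differ, so yes.
- High-frequency vs sham: criteria differ, so yes.

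**5. Cost of requiring both target types before randomization.** With failure p for each polarity, assumed independent, the share not randomized is 1 − (1 − p)²:
- p = 5%: 1 − 0.9025 = 9.75%, about 10%; 30 / 0.9025 = 33.2, so 34 consents for 30 randomized
- p = 10%: 1 − 0.81 = 19%; 30 / 0.81 = 37.04, so 38 consents

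If consents stay at 30, about 27.1 or 24.3 are randomized.

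**The case against.** **The event may never happen.** The plan intends a target for every subject, one discrete region is enough, and most of the frontal, parietal and lateral temporal cortex is available. Nothing in the documents shows that targets fail. This stands, and it is why the rates above are assumptions. It does not remove the gap, because loss before session 1 for any other reason meets it too.

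**No one is said to be dropped.** A reader might infer that the plan excludes such subjects. It does not say so. The analyses are described as expected, intention to treat is the stated principle, and other handling of missing values is not ruled out. All subjects are also asked to keep diaries of seizures, and the Overview promises EEGs for all. The supportable claim is that handling is unspecified. The general diary request does not set a follow-up window, and the EEGs are still timed by the sessions.

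**The comparison with sham is not compromised as a whole.** This stands. Low-frequency vs sham shares one target criterion, so only the two comparisons that involve Group 2 could suffer arm-dependent loss.

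**The Data Analysis text could imply later randomization.** It describes imaging and then says that the cohort will be randomized. Subject Enrollment, items 1 and 4, and Stimulation target creation settle the order as randomization first. That wording needs aligning and is not a second rule.

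**Requiring both targets narrows the population.** This also stands. B1 aims to widen access to rTMS, and the restriction works against that. It is a real cost, set against a bias that is possible but not shown.

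**Conclusion.** The concern holds in this form: randomization precedes imaging, the baseline period and arm-dependent target creation; outcome dates depend on rTMS; and handling of a randomized but untreated subject is unspecified. The planned ANOVA cannot use a subject without a follow-up value, and this conflicts with the stated intention to treat.

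The timing and the dating gap rest on the text itself. The frequency does not: the percentages depend wholly on the assumed rates, and on whether all arms or only Group 2 are affected. A reader might go further and infer that the efficacy comparison is biased, or biased in a particular direction. The documents give neither a failure rate for each polarity nor any sign of which would fail more often, so unequal loss by arm is a possibility and no direction is claimed.

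**What to change.** **Preferred.** Keep the visit order, and move randomization to after the baseline diary, target creation and the pre-rTMS EEG, just before session 1. Outline a correlated and an anti-correlated accessible target for every subject before the arm is assigned, and randomize those who have both. Target failure and other losses before session 1 then occur before randomization, and targets are drawn with the arm unknown.

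The cost is a protocol amendment, one extra outline per subject (B3.A already maps both polarities), a population limited to patients treatable in any arm, and fewer randomized than consented: about 10% fewer at 5% failure per polarity and 19% at 10%, assumed independent. The amendment should state both numbers.

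**If randomization stays at consent.** For every randomized but untreated subject, obtain the baseline EEG at the end of the diary, run the 12-week follow-up diary and final EEG from a planned session-10 date fixed in advance, and analyse the subject in the assigned arm. This costs two EEGs and a diary per such subject and dilutes the effect. If untreated subjects do not change (assumed), the 56% reduction in an active arm becomes 56% × 0.95 = 53% at 5% failure and 56% × 0.90 = 50% at 10%. An untreated subject also knows that no session was given.

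**Either way,** align the B3.A Overview, Subject Enrollment, items 1 to 7 and the outcome paragraph after them; the B3.B Sample Size Justification, Data Analysis and Stimulation target creation; and Subject Selection (B3.C).
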